# 2.2 Significance

If C-RFA of the articular sensory nerve supply of the knee is found to decrease post-operative opiate consumption, provide meaningful pain relief and enhance post op physical therapy, the procedure can be integrated into the TKR perioperative treatment algorithm. Such treatment, if successful, will ultimately improve short and long term pain outcomes, patient satisfaction, and decreased length of hospital stay in a cost effective manner.

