## Statistical Analyses:

Baseline characteristics (e.g., sociodemographic variables, primary and secondary outcomes) will be compared between treatment groups using t-tests or chi-square tests for categorical variables. We will conduct intent-to-treat (ITT) analyses for all primary and secondary outcomes

using a series of generalized mixed-effects regressions. All statistical tests will be two-sided with significance set at  $p\leq.05$ . SAS statistical software version 9.2 (SAS Institute Inc., Cary, NC, USA) will be used for statistical analyses.

In preliminary analysis, the distributional aspects of the variables under consideration will be examined through descriptive statistics. These statistics will include measures of location (mean, median, quartiles) and measures of dispersion (range, standard deviation, variance) for continuous variables and frequencies of the levels of categorical variables. These measures will also assist with a data cleaning/screening procedure to eliminate any possible copying, handling, recording or measurement errors. In addition to the features described above, the dependence of outcome measures will need to be properly accounted for in the data analysis as measures will be made at multiple times for the same participant. Consequently, these observations tend to be correlated and require statistical techniques that can properly account for the correlation in order to draw valid inference. Our general approach for analyzing these multiple types of data in this trial will be the Generalized Linear Mixed-Effect Models (GLMM).

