### 4.0 Data Analysis:

Primary outcome:

• Between-group difference in analgesic use (MQS III score) at 48 hours.

Secondary outcomes: Between groups at 48 hours, 1, 3, 6 months in:

- 1. Visual Analog Scale for pain (at rest, with mobilization or weight bearing)
- 2. Knee Society Scale (clinician); WOMAC (patient)
- 4. Physical therapy milestones
  - a. Time to active SLR
  - b. Time until patient can get out of bed
  - c. Time until patient able to ambulate < 100 feet
  - d. Time until patient able to ambulate around room > 100 feet

e. Time until patient is able to climb stairs (quantify specifics, how many steps are considered appropriate?)

- 5. Patient Global Perception of Change (GPC)
- 6. Patient Satisfaction (Likert scale)
- 6. Hospital Anxiety and Depression Score (HADI)
- 7. SF12
- 8. McGill Pain Questionnaire

9. Inpatient length of Stay (LOS; days) and Physical Therapy "clearance for discharge" (days)

- 10. Complications of the injection procedure
- 11. Medication related adverse events (i.e. sedation, nausea, pruritus, delirium)

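### Every secondary comparison is tested at two-sided p≤.05 with no order, key outcome or supportive label: about 18 to 45 tests, and 0.9 to 2.25 chance findings expected if C-RFA does nothing

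*Combined protocol and SAP*

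**What the plan says.** The Statistical Analyses section sets the scope, "We will conduct intent-to-treat (ITT) analyses for all primary and secondary outcomes", and then one rule: "All statistical tests will be two-sided with significance set at" p≤.05. It makes generalized linear mixed-effects models (GLMM) the general approach because participants are measured repeatedly. It does not say which contrast is tested: an overall group effect, a group-by-time interaction, or a group difference at each visit.

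Section 4.0 names one primary outcome, analgesic use at 48 hours. The rest come under "Secondary outcomes: Between groups at 48 hours, 1, 3, 6 months in". The list includes "Visual Analog Scale for pain (at rest, with mobilization or weight bearing"), which is two scores, "Knee Society Scale (clinician); WOMAC (patient"), again two, "Patient Global Perception of Change (GPC") and "Patient Satisfaction (Likert scale"). It goes on to HADS, SF-12, McGill, five therapy milestones, length of stay, therapy clearance, injection complications and medication adverse events.

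Section 4.2 adds two-group tests of outcome measures, without saying whether they are run at each visit. No section gives a multiplicity adjustment, a testing order, a key secondary outcome or an exploratory label.

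**The concern.** A single threshold applied to a long unranked list lets any secondary result at or below .05 be called significant on the plan's own terms. Some chance results are then expected even if the treatment does nothing, and the plan does not say in advance which comparison would settle a question about pain or about rehabilitation.

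This matters because both topics are central to the trial's purpose. The research question in section 1.1 asks about pain scores as well as analgesic use, and section 2.2 looks forward to pain relief and better physical therapy. Pain alone offers eight VAS comparisons (two scores at four times). Rehabilitation offers seven (five milestones, length of stay, clearance). The issue remains even with analgesic use as the sole primary outcome.

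**Working it through.** **The plan's own figure.** The documents give no count of secondary tests and no error rate for them. The only related figure is the sample size in Statistical Power: 28 per group for a difference of 15 ME, SD 19, power .81, two-sided alpha .05, Mann-Whitney.

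- Two-sample normal formula: n = 2(1.960 + 0.878)² × 19² / 15² = 25.8 per group.
- Divided by the Mann-Whitney efficiency 3/π = 0.955: 27.1, rounded up to 28.

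The figure reproduces. It concerns analgesic use only; no secondary comparison was sized.

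**Counting the secondary tests (section 4.0).**

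- Repeated scales: VAS at rest, VAS with mobilization, Knee Society, WOMAC, global change, satisfaction, HADS, SF-12, McGill = 9.
- One-off outcomes: 5 milestones + length of stay + clearance + complications + medication events = 9.
- One overall group test per outcome: 9 + 9 = 18.
- Scales compared at each of four times: 9 × 4 + 9 = 45.

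Each scale is counted once. Subscales would add to either count.

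**Expected chance findings under no effect: k × .05.** This does not depend on correlation.

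- 18 × .05 = 0.9, about 0.45 favouring C-RFA.
- 45 × .05 = 2.25, about 1.1 favouring C-RFA.

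**Chance of at least one: 1 − .95^k if independent.**

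- k = 18: 1 − .95^18 = 60%.
- k = 45: 1 − .95^45 = 90%.

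The documents give no correlations, so I simulated correlated test statistics over an assumed range.

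| Correlation (between outcomes / within a scale over time) | 18 tests, any | 18 tests, favouring C-RFA | 45 tests, any | 45 tests, favouring C-RFA |
|---|---|---|---|---|
| 0 / 0 | 60% | 37% | 90% | 68% |
| .2 / .5 | 56% | 29% | 81% | 47% |
| .4 / .6 | 45% | 23% | 67% | 35% |
| .6 / .8 | 34% | 17% | 47% | 24% |

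The within-scale value applies only to the 45-test reading.

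**Selection within a topic.** One prespecified test favours C-RFA by chance 2.5% of the time. From independence through the assumed correlations, the best of eight VAS comparisons does so in about 18% to 9% of trials, and the best of seven rehabilitation outcomes in about 16% to 10%.

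**The case against.** **The count.** A reader might infer that 45 is a minimum. It is not. The GLMM is the stated general approach, and one overall test per outcome gives 18. Section 4.2 does not settle the matter. The time list heading the secondary outcomes supports the per-visit reading but, read literally, also covers milestones and length of stay, which have no visits. The range is therefore 18 to 45, and this part of the objection stands.

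**Adoption.** A reader might also infer that adoption could rest on whichever test crosses .05, because section 2.2 says that if C-RFA is found to decrease opiate use, "provide meaningful pain relief and enhance post op physical therapy, the procedure can be integrated" into care. The documents do not support this. The sentence is background, not a decision rule, and its three conditions must all hold. Even if any VAS test and any rehabilitation test may count, the chance under no effect that all three favour C-RFA is about 0.07% if independent and about 0.3% to 1.3% under the same assumed correlations.

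**Direction and safety outcomes.** About half of the chance findings would favour sham. Two of the outcomes are safety outcomes, which carry no efficacy claim, and rare events would have a true error rate below .05. Both points are right and modest in effect.

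**Convention.** There is one primary outcome, the trial is sized on it, and everything else is called secondary. The plan nowhere says that a secondary result will be treated as confirmatory. But it gives secondary outcomes the same significance rule as the primary and no label that limits how such a result may be used, so convention does not close the gap.

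**Conclusion.** The point holds as a should-fix matter for the secondary outcomes only. Followed as written, the plan produces 18 to 45 significance statements with no control over them. Under no effect it should be expected to yield 0.9 to 2.25 significant results, roughly half in favour of C-RFA. These expectations rest only on the count and the .05 threshold. The chance of at least one is 60% to 90% under independence and about 34% to 81% under the assumed correlations, which the documents neither give nor contradict.

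The primary comparison and its power are untouched. What is exposed is a stand-alone claim on pain or on rehabilitation, chosen after the fact from several candidates.

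**What to change.** In Statistical Analyses and section 4.0, state that the 48-hour between-group analgesic comparison is the only confirmatory test at .05. Report all secondary outcomes as estimates with 95% intervals, labelled supportive, with no significance claim.

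If the sponsor wants a confirmatory claim on pain or rehabilitation, it should name one comparison for each before unblinding and test them in fixed order at .05, only after a significant primary result. Which comparisons to name is the sponsor's choice; the documents give no basis for preferring particular ones. Fixed-order testing needs no split of alpha, so the primary test's power and the sample size stay as they are. The GLMM contrast should be stated at the same time, so that the number of comparisons is known.

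The cost is wording. The sponsor gives up significance claims on the other secondary comparisons.

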## Statistical Power

The power analysis for this study was performed using data from Choi et al and assumptions regarding perioperative opiate requirements in patients undergoing TKR without an indwelling epidural catheter or peripheral nerve block. A sample size of 28 per group is needed to detect a difference in analgesic use of 15 morphine equivalents (ME) per 24 hour cycle, assuming the controls use 47 ME per 24 hours cycle with a standard deviation of 19 ME with a power of .81 at alpha = 0.05. The sample size calculation was computed using a two-sided Mann-Whitney Test (PASS). To correct for lost to follow up and dropout rates, we will recruit 30 patients into each treatment group.

Duration of follow-up This trial is designed with 6-month duration of follow up after surgery.

### Use of only one exposure to the intervention

We will not allow repeat injections for either treatment group. No patients will receive intraarticular or peri-articular steroids in this study.

Blinding In the current proposal, [name] is responsible for performing all of the active C-RFA and sham control procedures. To accommodate proper blinding, identical auditory, visual and tactile experiences for both treatment groups will be maintained. We will use deception to protect blind. The proceduralist will be blinded to all follow-up data until the study is completed. Similarly, the research assistants who perform all follow-up data will be blinded to group assignments until the conclusion of the study. We will also query patients at the 3-month follow-up to assess their beliefs on what treatment they believe they had and whether they would recommend the treatment to a friend.

Maintaining Confidentiality The data will be collected and stored in a password-protected computer located in the Department of Anesthesiology. Participants will each be assigned an ID number, which will be used as the sole identifier on any documents. Subject data will be compiled onto a single password protected file, where they will only be identified by their ID number.

[figure not shown]
An enrollment log will be the only file where subject names are correlated with ID numbers. This will be kept in a separate, secure, password-protected file in compliance with HIPPA and hospital policy within the Department of Anesthesiology.

The randomization assignment will be kept in a binder in a locked cabinet in the pain clinic. A copy of the randomization table will kept in a separate, secure, password protected file on a computer located in the department of anesthesiology.

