To date, few publications have demonstrated the use of RFA for knee pain from OA. Choi et al used conventional RFA of the articular nerves in the knee in elderly patients with chronic knee pain from OA in a double blind randomized controlled trial published in 2011. RFA at three nerve locations was performed with image guidance and each lesion was performed at 70 degrees C for 90 seconds with a 22 gauge cannula. Needle placements were at the region connecting the shaft of the femur to the bilateral epicondyles (superior lateral and superior medial genicular nerves) and the shaft of the tibia meeting the medial epicondyle (inferior genicular nerve). Patients who underwent RFA reported at least a 50% decrease in pain scores at one and three months following the procedure, whereas the sham control group had no demonstrable change in pain at these time points. Oxford knee disability scores and patient satisfaction scores were also significantly improved in the RFA group but unchanged in the control group. No adverse events were reported in the 38 patients enrolled in the study. In a single case report, conventional RFA of periarticular nerves in a patient with chronic knee pain following TKR was described with favorable clinical results and drastically improved pain control, but the RFA was performed remote to the time of the TKR for the indication of chronic pain, not to treat perioperativ pain in the immediate postoperative and rehabilitative periods.

Thus, although RFA has been used in patients with chronic knee pain from OA and in one case treating chronic pain many months following knee replacement, C-RFA has not been used in the perioperative management of pain in patients undergoing total knee joint replacement surgery.

The aim of this study is to determine if patients undergoing unilateral total knee replacement obtain any pain relieving benefits from C-RFA of the articular sensory nerve supply prior to surgery, as compared to sham controls who receive only local anesthetic injections of these same nerves without the benefit of ablation treatment.

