#### Participants

Inclusion criteria include:

- 1) Adults 30 to 80 years old
- 2) OA of the knee scheduled to undergo their first unilateral knee joint replacement
- 3) Willingness to undergo fluoroscopy-guided C-RFA or sham treatment.

Exclusion criteria include:

- 1) Conditions that preclude C-RFA or sham intervention (e.g. pregnancy, severe cardiac/pulmonary compromise; acute illness/infection; coagulopathy or bleeding disorder; allergic reactions/contraindications to a local anesthetic).
- 2) Prior TKR on either knee
- 3) Inability to write, speak or read in English
- 4) Patient refusal

Recruitment

Site(s) where study will be performed: Department of Anesthesiology, [name] Department of Orthopedic Surgery, [name] Patients who schedule a primary unilateral TKR with their orthopedic surgeon at NM will be asked to participate in the study by authorized research personnel. They will be screened to determine candidacy for the study; if they meet eligibility criteria, they will read and sign an informed consent form to participate. Each participant will be scheduled to see [name] in the Pain Medicine Center for the intervention procedure. They will be asked to be NPO for this visit and arrange a driver to accompany them home. This procedure will be performed 2-4 weeks prior to their planned knee surgery. The research assistant will calculate Morphine Equivalents (ME) of all analgesic medications including opiates, anti-inflammatories and membrane stabilizers.

Each participant will complete the following written outcome measures prior to the intervention: It will take approximately 10 minutes to complete the questionnaires.\* VAS pain score WOMAC questionnaire SF12 questionnaire Hospital Anxiety and Depression Inventory questionnaire McGill Questionnaire

Following the intervention procedure the following data points will be recorded: VAS pain score PGIC Questionnaire Patient satisfaction

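### The eligibility criteria do not exclude, and the baseline data do not record, earlier genicular nerve ablation of the index knee, so a sham patient may reach surgery with the target nerves already ablated.

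*Combined protocol and SAP*

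**What the plan says.** All references are to the combined protocol and SAP.

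- **Participants (section 3.0)** has three inclusion and four exclusion criteria. On earlier knee procedures it excludes only "Prior TKR on either knee". The criterion on conditions that preclude the procedure gives as examples pregnancy, cardiac or pulmonary compromise, acute illness or infection, bleeding disorders and problems with local anesthetic. The baseline data are VAS, WOMAC, SF12, the hospital anxiety and depression questionnaire, McGill, and analgesic use in morphine equivalents (ME).
- **Use of only one exposure to the intervention** states: "We will not allow repeat injections for either treatment group". The next sentence rules out joint steroid injections during the study.
- **Section 2.1 Background** describes the controls as patients who receive local anesthetic at the same nerves but no ablation. Of a trial of conventional RFA in chronic osteoarthritic knee pain it reports: "Patients who underwent RFA reported at least a 50% decrease in pain scores at one and three months following the procedure".
- **Statistical Power** sizes the trial at 28 per group for a difference of 15 ME per 24 hours, "assuming the controls use 47 ME per 24 hours cycle with a standard deviation of 19 ME", "with a power of .81 at alpha = 0.05", by a two-sided Mann-Whitney test. Thirty per group are to be recruited.

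**The concern.** The trial enrols people whose knee osteoarthritis has led to replacement surgery. By the protocol's own account, ablation of these nerves has been tried for chronic pain in that disease, with relief at one and three months. Someone who had it shortly before screening meets every criterion as written. Having had an ablation does not prevent either study procedure, so the criterion on precluding conditions does not catch it.

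Such a patient allocated to sham may already carry some of the effect that the trial is meant to measure. In the active arm, the same patient is treated a second time and may gain little. Either way the contrast between arms narrows. Because ablation history is not among the listed data, and neither stratification nor adjustment for it is planned, these patients could not be identified at analysis and no sensitivity analysis could set them aside.

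**Working it through.** **1. Can an earlier effect still be present at surgery?** The study procedure takes place 2 to 4 weeks before surgery. A patient ablated about 4 weeks before the study procedure would be 4 + 2 = 6 to 4 + 4 = 8 weeks out at surgery, inside the three-month period of relief reported in section 2.1. At about 8 weeks before, the figure is 10 to 12 weeks, near the end of that period.

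**2. Reproduce the plan's power.** Inputs from Statistical Power: means 47 and 32 ME (47 − 15), SD 19, n = 28 per group, two-sided alpha 0.05. For normal data the Mann-Whitney test has efficiency 3/π relative to the t-test, so the effective n is 28 × 3/π = 26.7. The noncentrality is (15/19) × √(26.7/2) = 2.89, and the noncentral t distribution gives power 0.809. Simulation of the Mann-Whitney test gives 0.807. The stated .81 is reproduced.

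**3. Add previously ablated sham patients.** Let *k* of the 28 sham patients have their mean shifted down by *s* ME, with the active mean held at 32 (no gain from a second ablation). The expected difference is 15 − *s* × *k*/28. Both *k* and *s* are assumptions, since the documents give neither. Power is simulated with a two-sided Mann-Whitney test at 0.05.

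| k of 28 | Difference, s = 15 | Power, s = 15 | Difference, s = 7.5 | Power, s = 7.5 |
|---|---|---|---|---|
| 0 | 15.0 | 0.81 | 15.0 | 0.81 |
| 1 | 14.5 | 0.77 | 14.7 | 0.79 |
| 2 | 13.9 | 0.74 | 14.5 | 0.77 |
| 3 | 13.4 | 0.71 | 14.2 | 0.76 |

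Repeat simulation runs differ by about one point.

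**4. Express it as a rate.** If a fraction *f* of patients was ablated earlier with full effect, the difference is 15 × (1 − *f*). By the method of step 2, power at 28 per group is:

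- *f* = 2%: 14.7 ME, power 0.79
- *f* = 5%: 14.25 ME, power 0.77
- *f* = 10%: 13.5 ME, power 0.72

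The number per group needed for power .81 rises from 28 to about 31 at 5% and 34 at 10%. Three ablated sham patients would correspond, under 1:1 allocation, to about 6 of 60 enrolled, or 10%.

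**The case against.** Four objections deserve an answer.

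- **The plan breaks no promise.** A reader might infer from the single-exposure heading that enrolling a previously ablated patient violates the plan's own rule. The text does not support that. The sentence under the heading concerns repeat injections, the next is limited to the study, and neither addresses history. This objection stands in full.
- **Earlier ablation may be rare.** The words "although RFA has been used in patients with chronic knee pain from OA" come from a sentence stressing how little had been done, and section 2.1 says that few publications exist, describing one 38-patient trial and one case report. No passage supports a rate near 10%. This stands, and it limits the size of the point.
- **The full 15 ME shift is an upper case.** The cited relief is of chronic pain after conventional RFA. An effect on analgesic use after knee replacement is the hypothesis under test, and section 2.1 says that C-RFA lesions are larger than conventional ones. The half-effect columns are therefore at least as relevant.
- **Validity is not at risk.** Allocation is randomised, so earlier ablation is balanced in expectation, although chance imbalance is possible with 30 per arm. The expected result is dilution, not a spurious benefit. Nor does the plan require an untreated baseline, since patients enter on their usual analgesics.

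None of this closes the gap. Balance between arms does not remove dilution, and a history that is never recorded cannot be examined later.

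**Conclusion.** The gap is real: as written, the criteria admit a patient whose target nerves on the index knee are already ablated, which does not fit the comparison stated in section 2.1. The consequence is dilution toward no difference, of unknown and probably small size.

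In the upper case, one such sham patient costs about 4 points of power and three cost about 10. At half the effect the losses are about 2 and 5 points. A reader might infer that a few such patients would exhaust the planned power. The figures do not show that, because even the worst case tabulated leaves about 0.71. The power statement itself is not in error.

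These figures rest on normal data, the plan's 47, 32 and 19 ME, 28 evaluable patients per arm, no gain from a second ablation, and ME per 24 hours standing in for the 48-hour primary outcome. Only the text supplied could be checked; the consent pages and one figure were not available.

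**What to change.** Add a fifth exclusion under Participants: *Previous radiofrequency ablation (conventional or cooled) or other neurolysis of the genicular nerves of the index knee.* Ask the question at the existing screening.

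The cost is one eligibility line, one history question, the loss of the few candidates affected and a slightly narrower population. The sample size stays as it is, because with no such patients the planned 15 ME contrast and power of about 0.81 are kept. The single-exposure section needs no change.

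If the sponsor prefers not to narrow the population, the lesser alternative is to record earlier ablation at baseline and specify an adjustment or sensitivity analysis. That makes the patients visible but does not restore the contrast.
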